9.3 Disease Parameters

Measurable Disease: Measurable lesions are defined as those that can be accurately measured in at least one dimension (longest diameter to be recorded) as ≥ 10 mm with diagnostic techniques (CT, or MRI). All tumor measurements must be recorded in millimeters (or decimal fractions of centimeters). Serial PSA measurements will also be analyzed.

Non-Measurable Disease: All other lesions (or sites of disease), including small lesions (longest diameter < 10 mm with diagnostic techniques), are considered non-measurable disease. Bone lesions, leptomeningeal disease, ascites, pleural/pericardial effusions, lymphangitis, abdominal masses (not followed by CT or MRI), and cystic lesions are all non-measurable.

Target Lesions: Target lesions in this study will be considered oligometastatic sites up to a maximum of 3 lesions per patient. They should be recorded and measured at baseline. Target lesions should be equal to or larger than 10 mm in the smallest cross-sectional diameter on CT or MRI and/or any lesion that shows

increase uptake on bone scans. A sum of the longest diameter (LD) for all target lesions will be calculated and reported as the baseline sum LD. The baseline sum LD will be used as reference by which to characterize the objective tumor response. For bone scans we will also use a simple evaluation system composed of positive, negative or no change to lesions.

Non-Target Lesions: N/A

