5.1 Inclusion Criteria

- 5.1.1 Patient must have at least one and up to three asymptomatic metastatic tumor(s) of the bone or soft tissue (with at least one bone metastasis) within the past 3-months that are ≤ 5.0 cm or <250 cm 3 as seen on either CT/MRI scan and/or bone scan. Up to five lesions are allowed on advanced functional imaging such as fluciclovine (Axumin), choline or ^{18}F -DCFPyL (“PyL”) PET-CT scan within the past 6-months. (PET-CT scan is reasonable for study entry imaging as an alternative to CT/MRI scan and/or bone scan)
- 5.1.2 Patient must have had their primary tumor treated with surgery and/or radiation.
- 5.1.3 Histologic confirmation of malignancy (primary or metastatic tumor).
- 5.1.4 PSADT <15 months. PSA doubling time (PSADT) will be calculated using as many PSA values that are available from time of relapse (PSA > 0.2). To calculate PSADT, the Memorial Sloan Kettering Cancer Center Prostate Cancer Prediction Tool will be used. It can be found at the following web site: <https://www.mskcc.org/homograms/prostate/psa-doubling-time>.
- 5.1.5 Patient may have had prior systemic therapy and/or ADT associated with treatment of their primary prostate cancer. Patient may have had ADT

associated with salvage radiation therapy (to the primary prostate cancer or pelvis is allowed).

5.1.6 PSA ≥ 0.5 but ≤ 50 .

5.1.7 Any testosterone lab within the past 6 months $> 50\text{ng/dL}$.

5.1.8 Patient must be ≥ 18 years of age.

5.1.9 Patient must have a life expectancy ≥ 12 months.

5.1.10 Patient must have an ECOG performance status ≤ 2 .

5.1.11 Patient must have normal organ and marrow function as defined as:

Before the first administration of Xofigo, the absolute neutrophil count (ANC) should be $\geq 1.5 \times 10^9/\text{L}$, the platelet count $\geq 100 \times 10^9/\text{L}$ and hemoglobin $\geq 10 \text{ g/dL}$.

5.1.12 Patient must have the ability to understand and the willingness to sign a written informed consent document.

5.1.13 LDH lab performed within 6 months of enrollment.

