6.11 Criteria for Patient Removal

Diagnosis of >3 bone and/or soft tissue metastases on entry imaging studies before SBRT/SABR. PSA >50 ng/ml before SABR. Progression as defined in section 9.5.5.

Radium-223 administration may be delayed by no more than four weeks for recovery of adverse events. In case of a treatment delay greater than four weeks, treatment should be discontinued. It is important to note that in general (unless otherwise agreed), in cases where study drug has been ordered, the time window is reduced to -3 days to + 3 days, due to decay. If administration has to be postponed more than 3 days after drug has been ordered, replacement of the drug order is required. Dose reduction for radium-223 will not be permitted and subjects with any toxicity requiring radium-223 dose reduction must discontinue radium-223 treatment.

Any toxicity requiring radium-223 discontinuation will be recorded as an AE in the subject's medical record and on the CRF.

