9.5.5 Clinical Response Parameters

Progression is a composite endpoint defined from the Prostate Cancer Working Group 2 (PCWG2) criteria for metastatic castrate resistant prostate cancer (mCRPC) (75) and our previous trials in a population of men with biochemical failure without metastases (72-74). Progression will be defined as either: 1) a $\geq 25\%$ increase in PSA from nadir (and by ≥ 2 ng/mL), requiring confirmation ≥ 4 weeks later (PCWG2 criteria); and/or, 2) clinical/radiographic-progression defined as symptomatic progression (worsening disease-related symptoms or new cancer-related complications), or radiologic progression (on CT scan: $\geq 20\%$ enlargement in sum diameter of soft-tissue target lesions [RECIST 1.1 criteria]; on bone scan: ≥ 1 new bone lesions), initiation of ADT or death due to any cause, whichever occurs first. Death is considered a severe adverse event here.

Progression Free Survival (PFS) is defined as the time from starting treatment to the time of progression as defined above. Subjects who do not progress will be censored at the time of the last contact.

ADT Free Survival (ADT-FS) is defined as the time from starting treatment to the time of initiation of palliative ADT. ADT will typically be initiated on tumor progression and/or development of new metastases. Subjects who do not start ADT will be censored at the time of the last contact.

Time to Progression (TTP) is defined as the time from starting treatment to the time of first documented tumor progression or new lesions by CT and/or bone scan or initiation of ADT. Subjects who do not progress will be censored at the time of the last contact. In addition, death from any cause will also be censored.

Time to New Metastasis (TNM) is defined as the time from starting treatment to the time of a new documented tumor metastasis by CT and/or bone scan. Subjects who do not progress will be censored at the time of the last contact.

Overall Survival (OS) is defined as the time from starting treatment until death due to any cause. For subjects who do not die, time to death will be censored at the time of last contact.

Locoregional Control (LRC) is defined as the time from starting treatment until local and/or regional relapse is documented

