14.5 Analysis of Secondary Objectives

- For safety analysis, adverse events will be summarized by type and grade.
- Kaplan-Meier (KM) estimates will be used to summarize ADT-free survival (ADT-FS), time to locoregional progression (TTLP), time to distant progression (TTDP), time to new metastasis (TNM) and duration of response over time. The median PFS, ADT-FS, TTLP, TTDP TNM and duration of response will be reported.
- The efficacy of SABR + Radium-223 in men with oligometastatic disease will also be determined by measuring local control of each lesion at 12-months.

Each metastatic lesion will be considered a target lesion and independently evaluated for response using RECIST 1.1 or bone scan evaluation criteria above. The lesion will be coded as being locally controlled if it is considered stable radiographic disease or if there is evidence of a partial or complete response. Local control assessment will start at three months following randomization and continuous assessment will be pursued during the follow-up period. The proportion of the lesions that have a stable or better response will be estimated using generalized estimating equation.

- Quality of life will be assessed using the Brief Pain Inventory form. An overall score will be calculated pre-treatment and at the time of the 2nd radiologic reassessment. The change in score will be evaluated with a paired t-test.

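### Growth of a known soft-tissue lesion outside the three-lesion target set has no radiographic progression rule, so it reaches PFS only through PSA, symptoms, ADT or death

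*Combined protocol and SAP*

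**What the plan says.** **Who enters.** Section 5.1.1 allows up to three lesions on CT/MRI and/or bone scan, at least one of them in bone. On PET the limit is higher: "Up to five lesions are allowed on advanced functional imaging". PET-CT may replace conventional imaging for entry.

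**Which lesions are followed.** Section 9.3: "Target lesions in this study will be considered oligometastatic sites up to a maximum of 3 lesions per patient". It adds: "Target lesions should be equal to or larger than 10 mm in the smallest cross-sectional diameter on CT or MRI", and/or any lesion with increased bone-scan uptake. It then says "Non-Target Lesions: N/A", and section 9.5.2 repeats N/A.

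**What counts as progression.** In section 9.5.5 the CT criterion is at least 20% "enlargement in sum diameter of soft-tissue target lesions [RECIST 1.1 criteria"]. The bone-scan criterion is at least one new bone lesion. A confirmed PSA rise, symptomatic progression, start of ADT and death also count. Section 9.5.1 scores the target sum, new lesions and PSA.

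**Local control.** Section 14.5: "Each metastatic lesion will be considered a target lesion and independently evaluated for response".

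**Lesion count elsewhere.** Section 6.11 lists as a ground for removal: "Diagnosis of >3 bone and/or soft tissue metastases on entry imaging studies before SBRT/SABR", without naming a modality. Section 14.1.1 describes the population as having three metastases or fewer.

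**The concern.** A lesion that is known at entry, and often treated, can fall outside the target set. There is no non-target category to catch it, and since it was already known it is not clearly *new*. The blinded radiologists of section 9.1 then have no rule under which its growth is progression.

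Three things are at stake:

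- **Timing and source of PFS events.** Failure at known disease may be recorded late, or through symptoms or ADT, which in an open-label trial rest partly on unblinded judgement.
- **Consistency between endpoints.** One growing lesion can be a failure for local control and a non-event for PFS.
- **Consistency between readers.** The text does not say whether a lesion known only on PET is *new* when it first shows on CT or bone scan, so two readers could score the same scan differently.

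**Working it through.** **1. Which lesions fall outside the target set?**

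- *By size.* A PET-positive node under 10 mm without bone-scan uptake cannot be a target. Nor can a node whose longest diameter reaches 10 mm but whose smallest does not, although 9.3 calls it measurable.
- *By the cap.* This matters less for PFS than it first appears, because 9.5.5 counts enlargement of soft-tissue targets only. Growth of any existing bone lesion, target or not, already lies outside its radiologic criteria. The protocol gives no order for filling the three slots. With b bone and s soft-tissue lesions, all otherwise eligible as targets, the number of soft-tissue lesions excluded is max(0, s − 3) if soft tissue goes first, and s − max(0, 3 − b) if bone goes first:

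| Total | b, s | Soft tissue first | Bone first |
|---|---|---|---|
| 4 | 1, 3 | 0 | 1 |
| 4 | 2, 2 | 0 | 1 |
| 4 | 3, 1 | 0 | 1 |
| 5 | 1, 4 | 1 | 2 |
| 5 | 2, 3 | 0 | 2 |
| 5 | 3, 2 | 0 | 2 |
| 5 | 4, 1 | 0 | 1 |

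With soft tissue first, the cap excludes a soft-tissue lesion in only one pattern (four soft-tissue lesions and one bone lesion).

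**2. Routes to a PFS event when such a lesion grows**

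| Route in 9.5.5 | Open? | Comment |
|---|---|---|
| CT, target sum +20% | No | Lesion is not in the sum |
| Bone scan, new lesion | Unclear | No rule for PET-known lesions |
| PSA | Yes | At least 25% and at least 2 ng/mL, confirmed at least 4 weeks later |
| Symptoms | Yes | Men enter asymptomatic (5.1.1) |
| ADT | Yes | Typically begun on progression or new metastases (9.5.5) |
| Death | Yes | |

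On PSA, the 2 ng/mL floor is the binding condition for any nadir below 2/0.25 = 8 ng/mL. Entry PSA may be as low as 0.5 (5.1.6).

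**3. Would lifting the cap alone be enough?** Take illustrative sizes: a fourth lesion grows from 12 to 24 mm beside stable targets. The protocol's sum changes by 0%. If the lesion were added to the sum:

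- target sum 30 mm: 54/42 − 1 = 28.6%
- target sum 45 mm: 69/57 − 1 = 21.1%
- target sum 60 mm: 84/72 − 1 = 16.7%

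The last is below 20%, so a doubling could still go unscored. A separate non-target rule is needed.

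**4. Effect on power.** Start with the plan's own figure (14.2: HR 0.5, one-sided alpha 0.1, 80% power, medians 10 and 20 months, 18 months' accrual plus 12 months' follow-up, 30 per arm).

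- Events needed (Schoenfeld): 4(1.2816 + 0.8416)²/(ln 0.5)² = 37.5, so 38.
- Event probability, assuming exponential PFS and uniform accrual, with λ = ln 2/median: 1 − [exp(−12λ) − exp(−30λ)]/(18λ) = 0.751 and 0.509, mean 0.630.
- Expected events: 60 × 0.630 = 37.8.
- Power: Φ(√37.8 × 0.693/2 − 1.2816) = 80.2%. The stated 80% reproduces.

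Now assume a fraction of events is lost outright, equally in both arms, with the HR still 0.5:

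| Events missed | Events | Power |
|---|---|---|
| 0% | 37.8 | 80.2% |
| 2% | 37.1 | 79.6% |
| 5% | 35.9 | 78.7% |
| 10% | 34.0 | 77.0% |
| 20% | 30.3 | 73.4% |

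**The case against.** The strongest reply is that PFS is a composite, and its PSA, symptom, ADT and death components are not tied to target lesions. That stands. A reader might infer that growth of an unlisted lesion can never be a progression event. The documents do not support this: such growth is captured indirectly and perhaps late.

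A reader might also take two of five lesions (40%) or one of four (25%) as the share unscored for PFS. That does not follow. Growth of existing bone lesions is outside the radiologic criteria whatever the cap, and the cap's effect on soft tissue depends on an unstated order of selection.

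Nor does section 9.3 set a competing denominator for local control. It defines a patient-level sum of diameters, while section 14.5 defines a separate lesion-level endpoint. What remains is that *target lesion* has two meanings, and that one lesion can fail under 14.5 without a PFS event.

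It can further be said that the cap of three agrees with sections 6.11 and 14.1.1, leaving the five PET lesions of 5.1.1 as the outlier. This shows that the lesion count is unreconciled. It does not close the gap, because a node under 10 mm is unscored even in a man with three lesions.

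Citing RECIST 1.1 in 9.5.5 does not help either. Whatever that standard provides for non-target lesions, 9.3 and 9.5.2 expressly set the category aside.

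Finally, the rule is the same in both arms and the readers are blinded, so no between-arm bias is shown. That also stands.

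**Conclusion.** The gap is real but narrow. Followed exactly, the plan gives the blinded readers no rule for growth of a known soft-tissue lesion outside the target set. Some progression will be delayed, or will be recorded through components that are less well protected from unblinded judgement.

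The size cannot be computed from the documents, because the share of men with small PET-positive nodes or more than three lesions is not given. The calendar notes place a PSMA PET/CT before enrolment as standard of care, which makes exposure plausible. Having a PET scan does not, however, show that a man has such lesions. Under the assumed loss of 5% to 10% of events, power falls to 78.7% or 77.0%. Events that are delayed rather than lost would cost less. The design has little slack (37.8 events expected against 38 needed), but the larger problem is ambiguous scoring of the primary endpoint.

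This reading takes 9.5.5 as the operative definition. Section 14.4 points to a section 9.6.2, which the protocol does not contain.

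**What to change.** 1. Keep one baseline list of every lesion present at entry, with imaging modality, size and class (target or non-target). Use it for PFS (9.3, 9.5.2, 9.5.5) and for local control (14.5).
2. Replace N/A in 9.3 and 9.5.2 with a rule that unequivocal progression of a known non-target lesion, called by the blinded radiologists of 9.1, is radiologic progression. Fix the threshold before the reads, and say whether the rule covers existing bone lesions, which 9.3 classes as non-measurable.
3. State whether a lesion known only on PET can count as new when it first appears on CT or bone scan.
4. If any limit on the number of targets remains, state the order in which lesions are chosen.
5. Reconcile the lesion count across 5.1.1, 6.11, 9.3 and 14.1.1. This review does not presume which figure is right.

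**Cost.** Protocol wording and a CRF lesion table, with no added scans or readers. The progression definition becomes slightly broader, so the 10-month control median assumed in 14.2 should be checked against it. Sections 6.11 and 6.15 use the same definition for removal and withdrawal, so the sponsor must decide whether the added event applies there too.

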9.4 Methods for Evaluation of Measurable Disease

All measurements should be taken and recorded in metric notation using a ruler or calipers. All baseline evaluations should be performed as closely as possible to the beginning of treatment and never more than 4 weeks before the beginning of the treatment.

The same method of assessment and the same technique should be used to characterize each identified and reported lesion at baseline and during follow-up. Imaging-based evaluation is preferred to evaluation by clinical examination when both methods have been used to assess the antitumor effect of a treatment.

Conventional CT, PET/CT, and MRI. These techniques should be performed with cuts of 10 mm or less in slice thickness contiguously. Spiral CT should be performed using a 5 mm contiguous reconstruction algorithm. This applies to tumors of the chest, abdomen, and pelvis. Head and neck tumors and those of extremities usually require specific protocols.

9.5 Response Criteria

9.5.1 Evaluation of Target Lesions/PSA Response

Complete Response (CR): Disappearance of all target lesions and PSA $<$ pre-SBRT PSA

Partial Response (PR): At least a 30% decrease in the sum of the longest diameter (LD) of target lesions, taking as reference the baseline sum LD. Or a third of the lesions are negative or no change by bone scan and PSA \leq pre-SBRT PSA.

Progressive Disease (PD): At least a 20% increase in the sum of the LD of target lesions, taking as reference the smallest sum LD recorded since the treatment started or the appearance of ≥ 1 new lesion(s). Or ≥ 1 new lesion(s) appear by bone scan. Or PSA $\geq 25\%$ increase in PSA from nadir or > 50 ng/ml.

Stable Disease (SD): Neither sufficient shrinkage to qualify for PR nor sufficient increase to qualify for PD, taking as

reference the smallest sum LD since the treatment started. Or PSA \geq pre-SBRT PSA, but not $\geq 25\%$ increase in PSA from nadir and <50 ng/ml.

9.5.2 Evaluation of Non-Target Lesions

N/A

9.5.3 Evaluation of Best Overall Response

The best overall response is the best response recorded from the start of the treatment until disease progression/recurrence (taking as reference for progressive disease the smallest measurements recorded since the treatment started). Best overall response will be based on the overall response of the target lesions.

9.5.4 Duration of Response

Response will be defined as evidence of CR, PR, or stable disease. The duration of response will be measured from the start of treatment until the criteria for progression are met.

Duration of CR or PR: The duration of CR or PR will be recorded from the time measurement criteria are met for CR or PR (whichever is first recorded) until the first date that current or progressive disease is objectively documented (taking as reference for progressive disease the smallest measurements recorded since the treatment started).

Duration of Stable Disease: Stable disease is measured from the start of the treatment until the criteria for progression are met, taking as reference the smallest measurements recorded since the treatment started.

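### Section 9.5.4 gives duration of response two incompatible definitions and section 14.5 reports one median without choosing; separately, the bone-scan limb of PR in 9.5.1 lets unchanged disease count as response

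*Combined protocol and SAP*

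**What the plan says.** The synopsis and sections 3.3 and 14.1.2 list duration of response as a secondary objective. Section 14.5 promises Kaplan-Meier estimates and one summary figure: "The median PFS, ADT-FS, TTLP, TTDP TNM and duration of response will be reported".

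Section 9.5.4 contains these rules:

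- General rule, responders: "Response will be defined as evidence of CR, PR, or stable disease".
- General rule, clock: "The duration of response will be measured from the start of treatment until the criteria for progression are met".
- CR/PR rule: "The duration of CR or PR will be recorded from the time measurement criteria are met for CR or PR", ending when progressive disease is objectively shown.
- SD rule: "Stable disease is measured from the start of the treatment until the criteria for progression are met".

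Section 9.5.1 gives PR a size limb (a 30% fall in summed diameters) and a bone-scan limb: "Or a third of the lesions are negative or no change by bone scan", joined to a PSA no higher than the pre-SBRT value. On bone scan, PD in 9.5.1 needs at least one new lesion.

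Section 9.2 restricts response classification to men with measurable disease at baseline who completed SABR and were re-evaluated. Section 9.3 calls bone lesions non-measurable, yet accepts any lesion with increased bone-scan uptake as a target lesion. Section 9.1 sets response imaging at 6 and 12 months after randomization.

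**The concern.** A man with CR or PR has two durations under 9.5.4, with different start dates, and he is pooled either with SD men or only with other CR/PR men. The plan promises one median and leaves the choice to whoever runs the analysis of an open-label trial.

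Neither rule is sound as written. The general rule credits a man with response from treatment start merely for not having progressed, so his duration is his own progression time. The CR/PR rule is the usual form, but it inherits a PR category that unchanged bone lesions can satisfy. Switching to it without repairing 9.5.1 would leave stable bone disease inside the responder group.

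At stake is the meaning of one published secondary figure, and whether a reader could compare it with duration of response elsewhere.

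**Working it through.** **Plan's own figure.** No number is given for duration of response. The only design figure is the power for PFS in section 14.2: medians 10 and 20 months, one-sided alpha 0.1, 30 per arm, 18 months' accrual plus 12 months' follow-up.

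- Events needed (Schoenfeld): (1.2816 + 0.8416)² / (0.25 × (ln 0.5)²) = 37.5, so 38.
- Expected events, exponential times and uniform accrual: 30 × (0.751 + 0.509) = 37.8.
- Power at 37.8 events: 80.2%.
- Dropout: 60 / 0.95 = 63.2, rounded up to 64 for equal arms.

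The stated 80% and 64 reproduce and do not depend on duration of response.

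**One man, two clocks.** Take a response first seen on the month-6 scan and progression on the month-12 scan. The CR/PR rule gives 12 − 6 = 6 months. The general rule gives 12 months less the lag from randomization to treatment. Section 6.8 allows up to 60 days (about 2 months) for SABR, so the result is about 10 to 12 months. The gap is about 4 to 6 months.

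**Medians under each rule.** Assumptions not in the documents: exponential progression times at the section 14.2 medians, clocks aligned with randomization, and every man free of PD at the first assessment (time t1) counted as a responder. The share remaining is 2^(−t1/median). By the memoryless property, the general-rule median is t1 + the PFS median, and the CR/PR-rule median (if all were CR/PR) is the PFS median.

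| t1 | Arm | Free of PD at t1 | Of 32 | General rule | CR/PR rule |
|---|---|---|---|---|---|
| 6 mo | SABR | 2^(−0.6) = 66% | 21 | 16 mo | 10 mo |
| 6 mo | SABR + Radium-223 | 2^(−0.3) = 81% | 26 | 26 mo | 20 mo |
| 3 mo | SABR | 2^(−0.3) = 81% | 26 | 13 mo | 10 mo |
| 3 mo | SABR + Radium-223 | 2^(−0.15) = 90% | 29 | 23 mo | 20 mo |

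The 3-month rows assume an earlier assessment than the scheduled imaging. The clock alone shifts the median by t1.

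A third reading uses the CR/PR clock for CR/PR men and the SD clock for the rest. The median then depends on the unknown CR/PR share. In the SABR arm with t1 = 6, simulation gives 14.7, 13.3 and 11.8 months at shares of 25%, 50% and 75%.

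These figures show the size of the shift and are not forecasts. With t1 = 6, both combination-arm medians fall about 26 months after treatment start, beyond the two-year follow-up.

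**End of the clock.** The general rule ends at progression without saying which kind. Section 9.5.1 has a 25% PSA rise from nadir. The 9.5.5 composite requires 25% and at least 2 ng/mL, confirmed, and adds symptoms, ADT and death. Section 9.5.5 states censoring for PFS, ADT-FS, TTP, TNM and OS. Duration of response has no stated censoring rule.

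**The PR rule.** Take three bone lesions, all unchanged, with PSA at or below pre-SBRT. The bone-scan limb is met (3/3 is more than a third), so PR applies. There is neither shrinkage nor growth, so the size wording of SD applies too. Now take one lesion unchanged, two worse and none new, with the same PSA. One in three still meets the limb, so this man could be coded PR, provided no other PD limb is met.

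**The case against.** The best defence reads the general rule in 9.5.4 as an umbrella, with CR/PR and SD as two sub-durations. Crediting stability may also be deliberate, since 14.5 counts stable disease as local control. That could justify reporting a disease-control duration. It does not say which quantity the single median in 14.5 is, or which start date a CR/PR man has.

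Two stronger readings are tempting, and the documents do not support them.

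- A reader might infer that the reported median duplicates time to progression. Under the CR/PR rule there is no duplication. Under the general rule the men with PD at first assessment drop out, so the median is longer than that of PFS (16 and 26 months against 10 and 20 in the illustration). TTP in 9.5.5 has no PSA component and censors deaths, whereas both candidate progression rules include PSA. Plain TTP is also not among the medians listed in 14.5. The nearest match is PFS as defined in 9.5.5.
- A reader might infer that the bone-scan limb applies widely because every man has a bone metastasis. Section 9.2 limits classification to men with measurable disease, which on its face excludes bone-only men. Section 9.3 pulls the other way by allowing bone-scan lesions as targets. The reach is unsettled.

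It is also fair that the second PR example is not compelled. If the worsening lesions are measured, a 20% rise in summed diameters would be PD, as would a PSA at least 25% above nadir even when it is below the pre-SBRT value.

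Finally, the endpoint is descriptive, with no test specified. That limits the consequence but does not remove the contradiction.

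**Conclusion.** The point holds as a contradiction in 9.5.4 that 14.5 leaves open, plus a separate misclassification in 9.5.1. The choice of clock moves a responder's duration by up to about 6 months with a first response scan at 6 months. The median figures rest on exponential times and on counting every non-progressor as a responder; the contradiction itself rests on the text alone.

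Under the general rule, the endpoint is essentially PFS among men without PD at first assessment and adds little to it. PR by bone scan overlaps SD, in a number of men that the documents do not allow one to estimate. The change should be made before the analysis.

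**What to change.** - **Sections 9.5.4 and 14.5:** use one definition for the reported median: CR or PR only, from first documented CR/PR to progression or death. State whether progression follows 9.5.1 or 9.5.5, and give the censoring rule.
- **SD:** report it separately, labelled as duration of disease control, from treatment start.
- **Section 9.5.1:** remove the unchanged category from the bone-scan PR limb and require improvement with no worsening lesion. Deleting the unchanged category alone is not enough, because one negative lesion with two worse would still meet a one-third threshold.
- **Analysis set:** name it in 14.5, and reconcile 9.2 with 9.3 so that it is clear whether men with bone-only disease are classified for response.

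The cost is a wording change in these sections and fewer men counted as responders, hence a less precise median. No added visits or scans are needed.
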